6.2.2.3 Sensitivity analyses of secondary efficacy variables

Sensitivity analyses of secondary variables except for clinical events will be performed in the FAS using the same methods as for the primary efficacy variables. If the baseline values of secondary endpoints are missing, then only multiple imputation will be applied for those subjects. Please see the details in section 6.2.1.4. In addition clinical events will be analyzed by using life table statistics and Kaplan-Meier estimates in FAS (only time scope up to week 26) and SAF.

6.2.2.4 Additional analyses of secondary efficacy variables

Percentage change in hs-TNT from baseline to week 20 will be summarized by treatment group and overall in PPS BNP. In addition to analyses comparing population means in the different dose groups, the number of patients in whom the individual change from baseline value crossed clinically meaningful thresholds will be reported in post-hoc analysis separately.

6.2.3 Exploratory efficacy variables and analyses

Exploratory efficacy variables include:

- Activity (duration, intensity) reported values and absolute change from baseline at 20 weeks. Variables as specified in appendices 9.1
- Echocardiographic parameters, as described in Section 9.4.1 of Clinical Study Protocol, measured values and absolute / relative change from baseline at 20 weeks
- Left ventricular ejection fraction (LVEF; %), measured values, number of patients in whom absolute change from baseline after 20 weeks is > 5%
- Mandatory biomarkers, measured values and absolute / relative change from baseline at 20 weeks, including
 - NT-proBNP (pg/mL), measured values and relative change from baseline at 20 weeks to assess elevated filling pressures
 - UACR, cystatin-C, NGAL for the evaluation of kidney function

- KCCQ and EQ-5D-5L, as described in Section 9.4.4.1 and 9.4.4.2 of Clinical Study Protocol. Frequencies of answers to individual questions will be displayed by treatment group and overall by visit. In addition, changes from baseline for the single questions will be categorized into the categories improvement / no change / worsening. Frequencies of the different categories will be displayed by treatment group and overall by visit.
The 7 individual domain scores and 3 summary scores of the KCCQ and their changes to baseline will be summarized by treatment group and overall by visit as continuous variables. The symptom stability domain (a measure of change in symptoms over the previous two weeks) and self-efficacy domain (a measure of patient knowledge how to prevent heart failure exacerbations and management of complications when they arise), will be reported and summarized but will not be considered measures of treatment efficiency. Change from baseline to week 20 of KCCQ domains of Physical Limitation Score, Symptom Frequency Score, Symptom Burden Score, Total Symptom Score, Clinical Summary Score and Overall Summary Score will be categorized into groups by 5 points and the number (%) of patients in each category of KCCQ domains respectively will be displayed by treatment group and overall. For scoring see Appendix, Section 9.3. The EQ visual analogue scale (VAS) values of the EQ-5D-5L and their changes to baseline will be summarized by treatment group and overall by visit as continuous variable.
- Time from randomization to all-cause mortality, non-fatal myocardial infarction, non-fatal stroke
- Change in NYHA class

Time to adjudicated clinical outcome events since randomization (using both separate and composite outcomes) will be described by means of life table statistics and Kaplan-Meier estimates in FAS. Other than time to event variables will be analyzed descriptively in FAS without missing data. In addition, percentage change in NT-proBNP from baseline to week 20 will be summarized by treatment group and overall. The percentage change of NT-proBNP from baseline to week 20 will be categorized into four groups (≤ -20 , > -20 to $\leq +20$, >20 and $\leq +30$, $> +30$). The number (%) of patients in each category of NT-proBNP respectively will be displayed by treatment group and overall.

6.3 Safety

The summaries of the safety data will be completed for the safety analysis population (SAF). No formal statistical test will be performed for the safety variables.

6.3.1 Extent of exposure

Study medication will be summarized for the safety population by treatment group, using descriptive statistics such as frequency and proportion (for categorical variables), mean, median, and standard deviation (for continuous variables).

All summaries related to intake of study medication will be by treatment group based on SAF:

- The treatment duration (date of last study medication- date of first study medication+1 day) will be summarized descriptively. Additionally the number of subjects by

treatment duration category will be given (≤ 28 days, $>28-\leq 56$ days, $>56-\leq 84$ days, $>84-\leq 140$ days).

- The time on study medication (treatment duration excluding days off study medication) will be calculated and summarized descriptively.
- The number of tablets taken will be summarized descriptively, as well as corresponding extent of exposure (total amount of intake in mg).

6.3.2 Treatment Compliance

Compliance is defined as $100 \times \text{number of tablets taken} / \text{number of tablets planned}$.

The compliance will be summarized descriptively by treatment group and overall. In addition, compliance will be categorized into three groups ($<80\%$, $80-120\%$, $>120\%$) and summarized by treatment group and overall.

6.3.3 Adverse events

All adverse events (AEs) will be coded according to the Medical Dictionary for Regulatory Activities (MedDRA) in its latest version which is specified in the TS domain.

A treatment-emergent AE is defined as any event arising or worsening after the start of study drug administration until 6 weeks after the last study medication intake.

Summary statistics (frequency and percentage of subjects) will be presented by treatment group using MedDRA for the following:

- Incidence rate of treatment-emergent AEs.
- Incidence rate of drug-related treatment-emergent AEs.
- Incidence rate of treatment-emergent AEs leading to death.
- Incidence rate of treatment-emergent AEs leading to permanent withdrawal of medication.
- Incidence rate of treatment-emergent AEs leading to interruption of medication.
- Incidence rate of treatment-emergent serious adverse events.
- Incidence rate of treatment-emergent drug-related serious adverse events.
- Incidence rate of adverse events of special interest:
 - Symptomatic bradycardia ($HR < 50$ bpm)
 - Findings in ECG and / or AVIVO device as follows:
 - ❖ Mobitz type I AV-block leading to withdrawal or interruption of study drug
 - ❖ Mobitz type II AV block leading to withdrawal or interruption of study drug or leading to any change in therapy
 - ❖ Third degree AV blocks

- Listing of treatment-emergent AEs leading to withdrawal: subject ID, investigator AE term, SOC, preferred term, start and stop date of study drug administration, start and stop date(relative days) of AE, drug related (yes/no), serious (yes/no), intensity, outcome.
- Listing of treatment-emergent serious AEs: subject ID, investigator AE term, SOC, preferred term, start and stop dates of study treatment, start and stop date of AE, drug related (yes/no), outcome, action taken.

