5.1 Design overview

Study 15128 is a randomized, double-blind, placebo-controlled, parallel group, multicenter, Phase II study. [Figure 5–1](#) displays the overall study design.

Figure 5–1: Study design overview

Abbreviations: CV = cardiovascular; ICF = informed consent form; W = week

Approximately 384 patients from approximately 90 study centers worldwide will be randomized to one of the active treatment dose arms or placebo, in addition to standard of care heart failure therapy (for details see [Section 7](#)).

The study will comprise a 1-week run-in period, 20-week treatment period, and a 6-week follow-up period (27 weeks total).

Patients will have site visits at weeks -1, 0 (baseline), 4, 8, 12, 20 (end-of-treatment visit) and 24 (safety follow-up visit). In addition, 2 phone calls at weeks 2 and 26 will be made to assess patients' safety, and one additional phone call - to remind the patients of AVIVO self-application at Week 19.

LVEF will be measured by echocardiography at baseline and end of treatment, NT-proBNP will be measured at baseline, Week 4 and end of treatment. Safety will be monitored throughout the study. PK samples will be taken from all patients at dedicated time points. Additional biomarkers reflecting the pharmacodynamic activity of the drug will be examined, as well as candidate biomarkers that may predict drug response.

For detailed visit descriptions and rules for patients who discontinue study treatment earlier, please see [Sections 9.1](#) and [9.2](#).

The anticipated duration of the study as a whole is approximately 19 months: this includes an anticipated recruitment period of 13 months followed by a run-in period of 1 week, a treatment period of 20 weeks and a follow-up period of 6 weeks after enrollment of the last patient into the trial.

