9.2.5 Visit 5 (Week 8)

- Physical examination (Section 9.6.3.2)
- Weight measurement
- NYHA class assessment (Section 9.4.3.2)
- Blood pressure and heart rate measurement (Section 9.6.3.4)
- Adverse events assessment (Section 9.6.1.3)
- Concomitant medication collection and recording (Section 8.1)
- AVIVO device application, worn for 7 days (Section 9.6.3.5)
- Blood sampling for safety (Section 9.6.3.1).
- PK sampling (pre-dose). Please note: on this day the patients should not take the study medication before the visit but only after the PK sampling. Ideally, the study personnel should contact the subject prior to Visit 5 to remind them not to take the study drug as usual in the morning at home. The patient should remember the time of the previous study drug intake as precisely as possible. Exact time of PK sampling and drug intake is to be documented in the patient's file.
- Study drug dispensing and unused study drug collection (Section 7.7)

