9.2.6 Visit 6 (Week 12)

- Quality of life questionnaire (KCCQ), to be completed by the patient (Section 9.4.4.1)
- PK sampling (Section 9.5):
 - Study drug is to be taken at home approximately 2 hours before the visit; it is important that the patients remember the time of study drug intake as precisely as possible; a phone call on the previous day to remind the patients is recommended. This information will be documented in the patient's file.
 - The first PK sample is to be taken approximately 2 hours after study drug intake (range 1:30 hour to 3:29 hours). Time of sampling should be precisely documented in the patient's file.
 - The second PK sample is to be taken approximately 4 hours after study drug intake (range 3:30 hours to 5:30 hours). Time of sampling should be precisely documented in the patient's file.
 - The minimum time between the two samples should be at least 1 hour.

If a patient does not take the study drug before the visit, he / she can take it at the start of the visit, in which case PK sampling will occur as described above.

- Physical examination (Section 9.6.3.2)
- Weight measurement
- 12-lead ECG (Section 9.6.3.3)

- NYHA class assessment (Section 9.4.3.2)
- Blood pressure and heart rate measurement (Section 9.6.3.4)
- Adverse events assessment (Section 9.6.1.3)
- Concomitant medication collection and recording (Section 8.1)
- Collection of AVIVO device applied at Visit 5 (Week 8)
- Handing-over AVIVO device to patients for self-application at Week 19 (Section 9.2.7) and instruction of patients how to apply the device
- Blood sampling for safety (Section 9.6.3.1)
- Study drug dispensing and unused study drug collection (Section 7.7)

9.2.7 Reminder phone call at Week 19

After 19 weeks of treatment (- 2 days) the site personnel will call the patients to remind them to self-apply the AVIVO device provided at Visit 6 (Week 12); if the device has not been provided at site, it should have been shipped to the patients. If there is an AE reported during the phone call, the investigator will have to make sure this is further assessed at the Week 20 visit or at an unscheduled visit prior to this.

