6.3.6 AVIVO/HealthPatch monitoring

AVIVO Mobile Patient Management System is intended to continuously measure, record and periodically transmit ECG data.

Notifiable ECG-findings (like AV-conduction abnormalities) triggered by system/patients based, as well as reportable ECG finding according to AVIVO will be summarized in frequency tables by treatment group. ECG-findings according to HealthPatch will also be summarized in frequency tables by treatment group. A table displaying the number of patients with AV-block > I° according to AVIVO/HealthPatch will be provided by treatment group. All patients with significant ECG-finding will be listed. The definition of the findings that trigger a notifiable report is in Appendices 9.1.

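### Treatment-emergent AE percentages pool unequal observation windows and device-finding counts lack a monitored-patient denominator, so unequal early stopping across doses could distort the dose comparison

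*SAP*

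**What the plan says.** SAP 6.3.3 defines a treatment-emergent AE as "any event arising or worsening after the start of study drug administration until 6 weeks after the last study medication intake". For the tables it says: "Summary statistics (frequency and percentage of subjects) will be presented by treatment group using MedDRA for the following". The lines that follow are called incidence rates, but the stated measure is a percentage of subjects. Protocol 9.6.1.1 uses the same 6-week limit. The line for AEs of special interest (symptomatic bradycardia and AV block) is the one incidence line that is not labelled treatment-emergent, and no window is given for it.

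For the monitoring device, SAP 6.3.6 plans frequency tables and says: "A table displaying the number of patients with AV-block > I° according to AVIVO/HealthPatch will be provided by treatment group". It states no denominator of patients monitored and no observation window. Observation follows the wear schedule in Protocol 9.1 and 9.2: 7 days from Week -1 (before dosing), Week 0, Week 8 and Week 19. The last period depends on "Handing-over AVIVO device to patients for self-application at Week 19". No device application is listed at the discontinuation visit, the safety follow-up visit or the Week 26 call.

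Related provisions:
- AEs are recorded to the end of follow-up (Protocol 9.6.1.3), and early stoppers keep the Week 26 call (Protocol 9.2.10).
- Treatment duration and time on drug are summarized separately (SAP 6.3.1).
- On-treatment clinical outcomes are right-censored at 6 weeks after the last dose in a Kaplan-Meier analysis (SAP 6.2.2.2).
- Unbalanced withdrawal across doses leads to further work on the primary variables only (SAP 4.3).

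**The concern.** A crude percentage compares arms fairly only if the arms are observed for similar lengths of time. Here the window shortens with early stopping, so an arm with more stopping has less time in which an event can count. The SAP already handles this same 6-week limit by censoring for CV death, HF hospitalization and urgent HF visits, but plans nothing equivalent for AEs.

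The device tables have a parallel problem by a different route. A patient who stops early misses later wear periods, and a count of patients with a finding does not show how many were monitored.

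What is at stake is the reading of safety across doses. Protocol 10.3.2.2 makes the final choice of target dose depend partly on safety considerations, and Protocol 3.4 names bradycardia and higher-degree AV block as the theoretical concerns of the mechanism. Some AEs of special interest are defined by withdrawal or interruption of study drug (Protocol 9.6.1.6), so stopping that rises with dose is plausible, though not shown.

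**Working it through.** **Figures in the documents.** They give no AE rate and no stopping rate by dose. The nearest figure, in Protocol 10.4, is that about 75% of randomized patients contribute complete data: 384 × 0.75 = 288, which reproduces. The other 25% includes invalid and missing data, so it is not a stopping rate. The stopping shares and event risk below are therefore assumptions.

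**Window per patient.** Completer: 140 + 42 = 182 days. Stopper at Week 4: 28 + 42 = 70 days. Stopper at a time uniform over Weeks 0-20: on average 70 + 42 = 112 days.

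**Mean window with stopping share s.**
- Uniform: 182(1 − s) + 112s = 182 − 70s.
- All at Week 4: 182(1 − s) + 70s = 182 − 112s.

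| s | Uniform, days | Shorter than s = 10% | Week 4, days | Shorter than s = 10% |
|---|---|---|---|---|
| 10% (placebo) | 175 | – | 170.8 | – |
| 20% | 168 | 4% | 159.6 | 7% |
| 30% | 161 | 8% | 148.4 | 13% |
| 40% | 154 | 12% | 137.2 | 20% |

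**Crude percentages with the same constant hazard in both arms.** Set the 26-week risk at 10%: h = −ln(0.90)/26 = 0.00405 per week.
- Risk for a Week 4 stopper (10 weeks at risk): 1 − exp(−10h) = 3.97%.
- Mean risk for a uniform stopper: 1 − [exp(−6h) − exp(−26h)]/(20h) = 6.25%.
- Crude percentage = (1 − s) × 10% + s × stopper's risk.

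| Stopping, placebo vs top dose | Uniform: crude % (ratio) | Week 4: crude % (ratio) |
|---|---|---|
| 10% vs 10% | equal (1.00) | equal (1.00) |
| 10% vs 20% | 9.63 vs 9.25 (0.96) | 9.40 vs 8.79 (0.94) |
| 10% vs 30% | 9.63 vs 8.88 (0.92) | 9.40 vs 8.19 (0.87) |
| 10% vs 40% | 9.63 vs 8.50 (0.88) | 9.40 vs 7.59 (0.81) |

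The shift is 0.4 to 1.8 percentage points; 1.8% of 64 patients is about one patient. The standard error of one comparison, √[a(1 − a)/96 + b(1 − b)/64] with the planned 96 placebo and 64 active patients, is about 4.5-4.7 points in these scenarios. At 10% vs 30% stopping, a true hazard ratio of about 1.09 (uniform) to 1.16 (Week 4) would show as equal crude percentages. Events per person-time in the same window give a ratio of 1.00 throughout, because the hazard was set equal and constant.

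**Device wear periods.** A completer has three on-drug periods (from Weeks 0, 8 and 19). A patient who stops before Week 8 has one, and a patient who stops between Weeks 8 and 19 has two.
- All stopping at Week 4: mean = 3 − 2s, giving 2.8 at 10% against 2.6 / 2.4 / 2.2 at 20 / 30 / 40% (7 / 14 / 21% fewer).
- Uniform stopping: a stopper averages (8/20) × 1 + (11/20) × 2 + (1/20) × 3 = 1.65 periods, so mean = 3 − 1.35s, giving 2.87 against 2.73 / 2.60 / 2.46 (5 / 9 / 14% fewer).

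**The case against.** The case against has real weight.

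- **The bias is conditional.** A reader might infer that doses with more stopping will look safer than they are. The documents do not support that as fact: they give no stopping rate by dose, and with equal stopping the ratio is 1.00. Every treated patient's window runs at least 6 weeks from first dose, barring death or loss, so events in that time count equally in all arms. This objection stands.
- **The 6-week rule does not govern the device tables.** SAP 6.3.6 states no such window and no percentage. What is missing there is the denominator of patients monitored. This stands, and it is why the two parts are kept separate.
- **AEs of special interest may not be cut at 6 weeks.** Their line is not labelled treatment-emergent, and AEs are collected to the end of follow-up. It would be tempting to assume that the bradycardia and AV-block table carries the same bias. The wording does not say so; it leaves the window open.
- **Much is already captured.** An event that causes stopping is counted, and appears again among AEs leading to withdrawal or interruption. Late deaths are tabulated (SAP 6.3.4), and the main HF outcomes have Kaplan-Meier estimates. Time to end of treatment is plotted by arm, AEs are listed individually, and an unblinded DMC reviews safety. The events lost occur more than 6 weeks off drug and say less about toxicity.
- **A person-time rate has its own bias.** If events cluster soon after the first dose, it inflates arms with more early stopping. This stands, and it shapes the fix.

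None of this supplies a time-adjusted AE summary by dose or a count of patients monitored in each wear period.

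**Conclusion.** The point holds as a conditional weakness in presentation, not as a demonstrated bias. Treatment-emergent AEs are compared as crude percentages over windows that differ with stopping, although the SAP censors clinical outcomes at the same limit. Device findings are counted without the number of patients monitored.

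The size rests on assumed stopping shares, equal and constant hazard, and infrequent events. The 7-20% range should not be read as typical: it puts all stopping at Week 4, and uniform stopping gives about 4-12%. Either way the distortion is below the sampling error of a single dose-placebo comparison. It matters because it runs in one direction if stopping rises with dose, and could flatten a descriptive dose trend used in choosing the dose. No endpoint, type I error or sample size is affected. Label: cheap improvement.

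**What to change.** Keep the crude tables and add the following.

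1. **SAP 6.3.3, treatment-emergent AEs and serious AEs:** cumulative incidence by dose, censored at the end of the treatment-emergent window with death as a competing event, and/or first events per 100 patient-years in that window. Note beside the rate that it assumes roughly constant hazard.
2. **SAP 6.3.3, AEs of special interest:** state the window that applies, and present them in the same way.
3. **SAP 6.3.6:** tabulate device findings by wear period, with patients having a recording in that period as the denominator. Give findings per recorded day only if recording time is available as an analysis variable; the SAP does not list it as one.

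The cost is a few sentences of SAP text and a few more tables. AE and dosing dates are already collected, but what counts as a recording in a wear period needs a definition. The downside is that the person-time rate can mislead if events cluster early, so it should not stand without the crude percentage or the cumulative incidence beside it.

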6.3.4 Deaths

Deaths reported during the study period will be tabulated by treatment group.

- Summary table of deaths (all deaths, all deaths during treatment and up to 6 weeks after last dose of study drug, all deaths later than 6 weeks after last dose of study medication)
- Listing of subjects who died during treatment and up to 6 weeks after last dose: subject ID, start and stop date of study medication, date of death, relative day and cause of death.

6.3.5 Clinical laboratory evaluations

All laboratory evaluations will be done by central laboratory.

Hematology: erythrocytes, hemoglobin, hematocrit, MCV, MCH, MCHC, reticulocytes, leukocytes, differential blood count, platelets

Clinical chemistry: aspartate aminotransferase (AST), alanine aminotransferase (ALT), alkaline phosphatase (AP), gamma glutamyl transpeptidase (GGT), lactate dehydrogenase (LDH), creatine kinase (CK), amylase, lipase, glucose, cholesterol (HDL, LDL, total), triglycerides, creatinine, urea, uric acid, bilirubin, total protein, albumin, sodium, potassium, calcium, chloride, magnesium, anorganic phosphate

Coagulation: partial thromboplastin time (PTT), international normalized ratio (INR)

The safety evaluation of laboratory data will include:

- Descriptive analysis of continuous laboratory parameters, and their changes from baseline by visit and treatment group.
- Incidence rates of treatment-emergent laboratory values outside of normal range by treatment group.
- Listings of laboratory data out of normal range.

Laboratory abnormalities will be summarized in table of change from baseline by visit and treatment:

- Change in renal function measured by eGFR change from baseline
- Change in liver function measured by bilirubin (total and fractions), AST and ALT from baseline

